One growing NCD is sarcobesity, which is characterized by reduction in muscle mass and increase in total and visceral fat mass, associated with mobility problems and/or the development of adipose-based chronic diseases (ABCD), especially type 2 diabetes, found in 80 to 85 percent of overweight/obese people. The mechanisms underlying the initiation and progression of sarcobesity are still largely unclear.

Advanced glycation end-products (AGEs) contained in foods consumed following WD are considered one of the molecular mediators in the initiation and promotion of metabolic dysfunction and NCD more generally (12). AGEs represent a heterogeneous group of nonenzymatic adducts between reducing sugars and the free amino groups of proteins, nucleic acids, and lipids, usually resulting in fluorescent derivatives (13,14). AGEs can result either from endogenous formation or from exogenous sources, that is, from the diet (dAGEs). Endogenous formation occurs during aging and/or under conditions of oxidative stress and hyperglycemia, whereas exogenous AGEs result from the consumption of foods rich in saturated fats, sugars, meat, and cheese (13). In addition, even the typical WD preparation methods, such as heat and dehydration, and processing methods, such as grilling and frying, induce additional generation of AGEs from the diet.

These, subsequent to consumption of these products thus prepared, can be absorbed by the gastrointestinal system and only in part eliminated in the urine (12), with a significant amount

SCDU di Endocrinologia

AOU Maggiore della Carità, [name],
[name] [contact]
(Reparto);; [contact]
[contact]

Direttore: [name]

accumulating in various tissues. The accumulation of AGEs can directly alter the structure and function of cross-link proteins in tissues and can induce tissue injury, leading to the generation of reactive oxygen species (ROS) and amplifying inflammation by interacting with their receptor, RAGE (13). Importantly, diet-derived AGEs remain in contact with tissues for a longer period of time than endogenous AGEs, contributing strongly to tissue damage (12).

AGE accumulation in skeletal muscle, blood, and skin is associated with sarcopenia in patients with diabetes and older adults (15,16), and RAGE signaling induces MW in several conditions, including diabetes and cancer (17,18). This has been demonstrated in some experiments in mice, which were fed a diet enriched with AGEs, reporting elevated levels of carboxymethyl-L-lysine (CML) in muscles, concomitant with low muscle mass and endurance (19). We also note how AGEs derived from fructose, a disaccharide found in abundance in WD, activate lipogenesis, metabolic reconfiguration, and mitochondrial dysfunction in muscles (20). Similarly, prolonged consumption of typical WD foods accelerates age-associated decline in muscles (21), and a short-term high-fat diet promotes denervation-induced MW by impairing mitochondrial function (22).

The direct role of WD and dAGE accumulation in the initiation of sarcobesity and the role of the dAGE/RAGE axis in inducing the WD-dependent metabolic alteration, as well as the role in MW, have not been investigated so far. In recent decades, natural products with traditional values have been tested in vitro and in vivo, demonstrating their medical properties. Recently, natural active metabolites have emerged as promising agents to reduce the harmful accumulation/activity of AGEs in many diseases (23). At the same time, there is a growing interest in the use of natural anti-obesity products to reduce obesity dependent ABCD by increasing energy expenditure and improving glucose homeostasis in muscles (24). Therefore, natural strategies to prevent or reduce the production and/or accumulation of dAGE could be useful in mitigating the impact of WD on metabolic health, preventing the progression of sarcobesity and maintaining muscle function.

These agents could augment the arsenal to enhance the ability to treat sarcobesity and ABCD (25).

STUDY PURPOSE

The study aims to explore whether a high level of diet-derived AGEs may mediate Western diet-related muscle loss, influencing the onset and progression of sarcobesity, predisposing to earlier and more severe metabolic consequences, including type 2 diabetes (T2D).

The primary objective of the study is to investigate how AGEs accumulation correlates with muscle loss in adult patients with obesity and type 2 diabetes or lipodystrophy with the aim of identifying possible targets to mitigate the metabolomic alterations caused by WD. Specifically, the levels of circulating AGEs in the skin and correlated with the stage of sarcopenia in a group of patients with

SCDU di Endocrinologia

AOU Maggiore della Carità, [name],
[name] [contact]
(Reparto);; [contact]
[contact]

Direttore: [name]

obesity and a T2D diagnosis will be evaluated. In addition, the relationship between disease duration and AGEs levels will be evaluated.

Secondary objective will be to analyze the obtained clinical data to identify metabolites and metabolic pathways responsible for the WD-induced phenotype.

The final aim of the study is therefore to investigate whether high AGE levels correlate with an earlier and/or more pronounced onset of sarcobesity, in conjunction with increased inflammation and oxidative stress.

STUDY DESIGN

Type of study

The present study is cross-sectional observational. The reference population is defined by patients with obesity and a diagnosis of T2D within 15 years of study entry or patients with type 2 diabetes concomitant with lipodystrophic syndrome. This population was chosen as being at high risk for sarcobesity.

Lipodystrophy includes a heterogeneous spectrum of genetic and acquired diseases, characterized by subcutaneous adipose tissue loss, ectopic fat accumulation, insulin resistance, metabolic and cardiovascular diseases, premature aging, sarcobesity and muscle pain, high-grade inflammation, epigenetic dysregulation, and mitochondrial dysfunction. Therefore, patients with T2D and lipodystrophy are found to be highly inflamed, as they generally have a more severe T2D phenotype, presumed to be sarcopenic, and have a high rate of endogenous AGE production. Therefore, patients with lipodystrophy concomitant with T2D will be enrolled as sarcopenic and obese subjects, which represent an excellent strategy for comparison with the diabetic population without lipodystrophy.

SUBJECTS AND METHODS

A total of 195 consecutive subjects afferent to the SCDU of Endocrinology at Eastern Piedmont University between April 2024 and April 2026 who meet the inclusion criteria will be included in the study.

Inclusion criteria:

1. Patients of both sexes
2. Subjects of legal age

SCDU di Endocrinologia

AOU Maggiore della Carità, [name],
[name] [contact]
(Reparto);; [contact]
[contact]

Direttore: [name]

3. BMI compatible with obesity and diagnosis of type 2 diabetes in good metabolic control (HbA1c < 7.5 %) within 15 years of study entry or diagnosis of lipodystrophy (included in the ECLip - Registry (eclip-web.org))

Exclusion criteria

1. Age under 18 years old
2. Secondary obesity or genetic diseases (Prader Willi syndrome, Down syndrome); metabolic and endocrine (Cushing's syndrome, hypothyroidism);
3. Subjects with: Intestine Bowel disease (IBD), cancer.
4. Established or planned pregnancy during the months of study participation

After reading the study information sheet (see Managing Informed Consent), patients will be enrolled only after signing the informed consent form.

Duration of the study:

The study will last two years corresponding to the enrollment period given the cross-sectional nature of the study.

Definition of sarcobesity indices

According to the ESPEN/EASO consensus statement [26], the following aspects will be considered for the diagnosis of sarcobesity:

1. Skeletal muscle functional parameters defined by muscle strength measured by hand grip strength (Hand grip strength HGS), chair test (seat-lift test five times; 30-second seat test), balance tests, and walking test and walking speed.
2. Body composition by bio-impedance analysis (BIA).

Specifically, the percentage of fat mass (%MG), detected directly by BIA, and the percentage of skeletal muscle mass relative to body mass will be considered for the definition of sarcobesity

Skeletal mass will be calculated as:

$$MS(Kg) = [(h^2/(BIA \text{ resistance}) * 0.401) + (sex * 3.825) + (age * 0.071)] + 5.102$$

Where h indicates height measured in cm, sex is a dichotomous variable that takes value 1 for males and 0 for females, and age is measured in years.

From this measurement, the percentage of skeletal muscle mass (%MMS) will be calculated
$$\%MMS = (MS \text{ (Kg)}) / (\text{Body mass (Kg)}) * 100$$

SCDU di Endocrinologia

AOU Maggiore della Carità, [name],
[name] [contact]
(Reparto);; [contact]
[contact]

Direttore: [name]

According to the guidelines, subjects with impaired musculoskeletal function parameters (HGS <16 kg for women and <27 kg for men or chair test >15 seconds for both males and females [27]), impaired %MG ($\geq 25\%$ for males and $\geq 35\%$ for females [28]) and impaired %MMS ($<35.6\%$ ($\leq 28.7\%$ severe sarcopenia) for men, $<28.4\%$ ($\leq 23\%$ severe sarcopenia) for females [29]).

Quantification of AGEs and collection of other information

For all patients included in the study afferent from the SCDU of Endocrinology of the AOU

Maggiore della Carità in Novara, following understanding and signing of consent, AGEs levels will be measured by skin fluorescence, using the "AGE reader mu" instrument (DS Medica, granted for free use by the PRIN 2022 project PI [name]).

AGEs will also be assessed at the plasma level in free form (ELISA, fluorescence assay) or bound to hemoglobin (HbA1c clinical practice test), discriminating in exogenous (dAGEs) and endogenous AGEs, respectively.

The following information of interest to the conduct of the study will also be collected.

Socio demographic characteristics: gender, date of birth, date of diabetes diagnosis (for diabetic subjects), and date of recruitment, anthropometric measurements, weight, height, calculation of body mass index (BMI), waist, hip, arm, and calf circumference, and body composition analysis through bio-impedance analysis (BIA).

Level of dietary inflammation calculated through the validated Dietary Inflammation Index (DII) and the Alternative Healthy Eating Index-2010 (AHEI-2010) derived from basal metabolic assessment by indirect calorimetry in the morning on an empty stomach.

Level of adherence to the Western diet (via food diary, recall of the last 24 hours, and validated food frequency questionnaire (EPIC)) as potentially related to the level of AGEs.

The level of physical activity, related to sarcopenia, estimated in MET using the IPAQ questionnaire.

Biochemical evaluation by hematochemical sampling and urine samples as per clinical practice (Blood glucose, complete blood count, HbA1c, AST, ALT, GTT, ALP, CPK, Total cholesterol, HDL cholesterol, Triglycerides, Uric acid, Creatinine, Microalbuminuria, urine test, 25-OH-Vit. D, Calcium, Phosphorus and QPE). Additional parameters of scientific interest will also be evaluated (IL-6, IL-10, IL-17, TNF-alpha, INF-gamma, Leptin and Adiponectin) Samples will be stored at the UPO Biobank (<https://biobank.uniupo.it/en/>). In addition, serum and plasma will be collected for metabolomic analysis, evaluation of cytokine profiles in serum and C-reactive protein, by multiplex assay.

SCDU di Endocrinologia

AOU Maggiore della Carità, [name],
[name] [contact]
(Reparto);; [contact]
[contact]

Direttore: [name]

Analysis

Biochemical parameters according to clinical practice will be analyzed at the clinical biochemistry laboratories of the Maggiore della Carità Hospital in Novara. Metabolomic analyses will be performed at the Center for Translational Research on Autoimmune and Allergic Diseases (CAAD) of the University of Eastern Piedmont. Evaluation of exogenous AGEs will be carried out at the laboratories of the University of Perugia.

Sample size

Given a first-type error α of 0.05 and a power of 80 percent, 195 subjects will be required to observe as significant the correlation between AGEs levels and the indices used to assess the level of sarcobesity of at least 0.2. Given the low prevalence of lipodystrophy and considering a one-year recruitment duration, it is planned to include approximately 35 subjects with lipodystrophy. The remaining 160 subjects will have diabetes and obesity. In addition, considering that the duration of diabetes may affect the levels of AGEs and sarcobesity, both subjects with diabetes for a long time (80 patients) and less than one year (80 patients) will be selected who can be considered comparable to pre-diabetes.

Statistical analysis

Descriptive statistics will be used to summarize the sociodemographic, anthropometric, clinical, and lifestyle-related information collected. Categorical variables will be summarized by absolute frequencies and percentages while numerical variables as mean and standard deviation or median and interquartile range if not normally distributed in accordance with the Shapiro-Wilk test and after observation of QQ-plots.

Pearson's correlation coefficient or the corresponding nonparametric Spearman's index and confidence intervals will initially be calculated in order to assess the correlation between the level of individual AGEs and MMS, MMSH, body composition parameters, and skeletal muscle functional parameters. Then linear regression models will be used in order to assess the relationship between AGEs and indices defining sarcobesity adjusted for age, sex, duration of diabetes, and other potential confounding factors such as inflammation, western diet adherence, and physical activity levels. The LASSO method will be used for the selection of variables to be included in the multivariable regression models.

Poisson regression models with univariable and multivariable robust variance will be used to estimate prevalence relative risks for the association between AGEs and patient characteristic with the presence of sarcobesity and corresponding confidence intervals.

SCDU di Endocrinologia

AOU Maggiore della Carità, [name],
[name] [contact]
(Reparto);; [contact]
[contact]

Direttore: [name]

An integration of clinical, biochemical data, AGE levels, and patient omics signatures will be performed to develop a multifactorial diagnostic model using multivariate statistical analysis (e.g., factor analysis, principal component analysis, cluster analysis, discriminant analysis, partial principal component analysis, logistic model) and data-driven approaches. Machine learning algorithms will be applied to prioritize and weight risk factors. These analyses will be performed with an in-house statistical consultancy already used by the group.

Expected Results

With this study, we expect to obtain more information and correlations between nutritional assessment and its impact on inflammation, definition, and progression of sarcopenia, obesity, and T2D, based on body measurements and clinical parameters. Through biochemical, hormonal, and metabolomic analyses performed on the biological samples, we expect to identify possible markers related to the presence of AGEs. In conclusion, the primary expected outcome would be to identify a positive correlation between AGE accumulation in at least one compartment (skin plasma, urine) and the severity of sarcopenia status, so that we can obtain a rapid and noninvasive to identify individuals at high risk of developing MW and identify correlations between AGE levels and other metabolic characteristics, including in lipodystrophic disease.

ETHICAL ASPECTS

The experimental protocol for human studies will be submitted to the Novara Interhospital Ethics Committee, registered on ClinicalTrial.gov before initiation, and conducted in accordance with the Declaration of Helsinki. All enrolled subjects will sign informed consent before participating in the study.

- *Ethical principles for medical research involving human subjects* (Declaration of Helsinki - World Medical Association, current version);
- European Union *Standards of Good Clinical Practice* (ICH/GCP);
- *Convention on Human Rights and Biomedicine* (Oviedo Convention of 04/04/1997);
- Italian codes of ethics for health professions and specific current national regulations on clinical trials.

Management of informed consent

An information sheet explaining the type of study, purpose, procedures, sample and data collection, and possible benefits and risks of the research is available. This information will be presented to interested persons, who will have the freedom to give consent or to be able to withdraw it when the study has already begun.

SCDU di Endocrinologia

AOU Maggiore della Carità, [name],
[name] [contact]
(Reparto);; [contact]
[contact]

Direttore: [name]

Management of sensitive data

The following European and national regulations are kept in mind:

- *Regulation (EU) 2016/679 of the European Parliament and of the Council of April 27, 2016 and subsequent amendments published in the Official Journal of the European Union 127 of May 23, 2018 (GDPR);*
- *Legislative Decree No. 196 of June 30, 2003 (Personal Data Protection Code), as amended by Legislative Decree No. 101 of August 10, 2018 on "Provisions for the adaptation of national legislation to the provisions of Regulation (EU) 2016/679."*
- *Privacy Guarantor, Provision setting out the requirements for the processing of special categories of data, pursuant to Article 21(1) of Legislative Decree No. 101 of August 10, 2018.*

DATA PROCESSING METHODS AND BIOLOGICAL SAMPLES

The study involves the collection of information related to lifestyles and diseases of the subjects involved. The biological samples and the attached personal/sensitive data collected will be immediately *pseudonymized* by random assignment of alphanumeric codes associated with the study and will be entered into the REDCap Management Software. The decoding of said alphanumeric codes will be in the possession of the responsible research investigator. Therefore, it will only be possible for the responsible research investigator to link the information and data obtained from the searches to a specific subject.

Personal data will be processed for the purposes set out in the project, in accordance with the principles of lawfulness, fairness, transparency, purpose limitation, minimization and accuracy of data (Art. 5 GDPR) in paper and electronic form by individuals authorized to process the data. The availability, management, access, storage, and usability of data is guaranteed by the adoption of technical and organizational measures to ensure adequate levels of security (Articles 25 and 32 GDPR). Only researchers involved in the study and authorized by the responsible research investigator will have access to the data.

Biological samples will be stored at UPO Biobank according to certified quality and security standards. The biological samples will be pseudonymized, and only UPO Biobank officials authorized to process the data, and only in cases of necessity, will be able to link the pseudonymization code of the samples to the sensitive data of the study participant. Researchers who will perform analysis on the collected samples will, therefore, have no way of associating them with the participant's identity. Aliquots of the biological samples, in pseudonymized form, may be released to the managers of the facilities that will perform the laboratory investigations. Any remainder will be returned to UPO Biobank.

SCDU di Endocrinologia

AOU Maggiore della Carità, [name],

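### Lipodystrophy patients are labelled sarcopenic and obese at entry while sarcobesity is defined by fat-dependent measurements, and the pooled Poisson models have no group term, so a between-group prevalence difference can pass for an AGE association

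*Combined protocol and SAP*

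**What the plan says.** The protocol gives two accounts of the lipodystrophy group.

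- **Type of study.** These patients are presumed sarcopenic, are expected to produce endogenous AGEs at a high rate, and "patients with lipodystrophy concomitant with T2D will be enrolled as sarcopenic and obese subjects". The same section describes lipodystrophy as "characterized by subcutaneous adipose tissue loss". That sentence goes on to list ectopic fat accumulation and sarcobesity among the features.
- **Inclusion criterion 3.** The obese BMI stands in the T2D branch, before the word or. The lipodystrophy branch asks only for a registry diagnosis.
- **Sample size.** Here "it is planned to include approximately 35 subjects with lipodystrophy", and "The remaining 160 subjects will have diabetes and obesity". Obesity is again attached to the T2D group alone.
- **Definition of sarcobesity indices.** Status rests on impaired function (grip strength or chair test), %MG of at least 25% in men or 35% in women, and %MMS below 35.6% in men or 28.4% in women. %MMS divides skeletal muscle mass by body mass. No exemption is made for lipodystrophy.
- **Statistical analysis.** Robust Poisson models, univariable and multivariable, relate AGEs and patient characteristics "with the presence of sarcobesity and corresponding confidence intervals". No lipodystrophy term, stratum or exclusion is named for these or for the linear models.

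**The concern.** The outcome of the Poisson models is presence of sarcobesity. For about 18% of the sample (35/195) the protocol offers both an entry label and a measured rule, and nothing guarantees that they agree. It does not say outright which one enters the model.

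Whichever status is used, sarcobesity prevalence may differ between the two groups for reasons unrelated to AGEs and muscle: the label makes it high by presumption, and the measured rule may make it low for lack of fat. The protocol also expects the groups to differ in AGEs. A pooled model without a group term turns two such differences into an AGE association. The sign of that artefact depends on how the 35 are classified, and one of the two signs is the positive relation that the Expected Results section hopes to find.

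**Working it through.** **1. The plan's own figure.** The sample size is for a correlation of 0.2 with α 0.05 and power 80%. By Fisher's z, two-sided: n = ((1.960 + 0.842)/atanh 0.2)² + 3 = (2.802/0.2027)² + 3 = 193.97, so 194. The stated 195 is reproduced within one subject and is not in dispute. It was not derived for the Poisson models.

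**2. How the measured rule responds to fat.** Body mass = lean mass/(1 − %MG/100), so %MMS = (muscle/lean mass) × (100 − %MG). With muscle and lean mass held fixed, less fat lowers %MG and raises %MMS. Body compositions below are assumed for illustration.

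| Case | %MG | %MMS | Body-composition criteria met |
|---|---|---|---|
| Woman, 45 kg lean, 18 kg muscle | 40 | 0.40 × 60 = 24.0 | both |
| Same woman | 20 | 0.40 × 80 = 32.0 | neither |
| Man, 60 kg lean, 27 kg muscle | 35 | 0.45 × 65 = 29.25 | both |
| Same man | 20 | 0.45 × 80 = 36.0 | neither |

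Muscle is identical within each pair. Lower muscle can still give a low %MMS: 16 kg in the same woman at 25% fat gives (16/45) × 75 = 26.7. She then fails on %MG alone. Grip strength and the chair test do not enter this arithmetic.

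**3. Effect on the pooled Poisson model.** Inputs from the protocol: 160 + 35 subjects, a robust univariable Poisson model, and higher AGEs in lipodystrophy (direction only). Assumed inputs: sarcobesity prevalence of 20% or 40% in the T2D group, AGE shift of 0.5 or 1 SD, and no AGE effect within either group. With 1000 runs per cell, the prevalence ratio per within-group SD of AGE (share of runs with p < 0.05) is:

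| T2D prevalence | AGE shift | All 35 present | 10% present | None present |
|---|---|---|---|---|
| 20% | 1 SD | 1.35 (93%) | 0.93 (9%) | 0.86 (20%) |
| 20% | 0.5 SD | 1.18 (40%) | 0.97 (6%) | 0.91 (10%) |
| 40% | 1 SD | 1.17 (67%) | 0.89 (25%) | 0.86 (41%) |
| 40% | 0.5 SD | 1.08 (23%) | 0.94 (12%) | 0.92 (15%) |

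A repeat with the same inputs gave 1.09–1.37 (24–91%) for all present and 0.89–0.97 (5–26%) for 10% present, which agrees up to simulation error. The verdict uses these ranges.

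Intermediate cases at a 1 SD shift:
- With 50% of the 35 present, the ratio is 1.16 (27%) against a T2D prevalence of 20%, and 1.03 (8%) against 40%.
- With equal prevalence in both groups it is 0.98 (5%) at 20% and 1.00 (about 5%) at 40%.

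With no AGE difference between groups (run at a T2D prevalence of 40%), the ratio is about 1.0 under every coding.

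**4. Does a simple change remove it?** With a lipodystrophy group term, or with the T2D patients alone, the ratio returns to about 1.0 with 4–8% of runs significant.

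**The case against.** The strongest reply is that the Type of study sentence only explains why a high-risk comparison group is recruited. The measured criteria apply without exemption, bio-impedance is listed for the patients included, and nowhere is the presumption said to replace measurement. This stands. A reader might infer that all 35 will be coded as cases by diagnosis, and that the largest false-positive rates therefore describe the plan. The documents do not support that; it is a bounding case.

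A reader might equally infer that the entry label and the measured rule give opposite outcomes for the same patients. That is not shown either. The protocol gives no BMI or %MG for lipodystrophy, calls it a heterogeneous spectrum and mentions ectopic fat, so some patients may well exceed the %MG cut-off. Nor is a result of absent a misclassification: the background section defines sarcobesity as reduced muscle with increased fat, so a patient without excess fat is correctly not sarcobese.

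Three further limits apply. The sentence stating the rule is incomplete, so that all components are required is inferred from its wording. Criterion 3 could be parsed with the BMI condition covering both branches, although Type of study and Sample size speak against it. The multivariable models might absorb part of a group difference through covariates such as inflammation, but the covariates named do not include lipodystrophy, and univariable models are planned as well.

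What remains is that the label and the rule are unreconciled, and that pooling without a group term is open to the artefact under either status.

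**Conclusion.** The concern holds as a conflict in wording plus an unprotected pooled analysis. The entry label should not stand beside a measured definition that depends on fat mass, and the Poisson models have no safeguard against a group difference in prevalence.

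Under the assumed values, the spurious prevalence ratio is about 1.1 to 1.4 per SD (24–91% significant) if all 35 count as present, about 0.9 to 0.97 (5–26%) if 10% do, and close to 1 if prevalence is similar in the two groups. The bias can therefore be large, small or absent. Only its mechanism follows from the documents. Its size rests on the assumed prevalence and AGE shift and on the univariable model, and the effect of fat loss on the measured rule is a direction of unknown magnitude.

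A reader might go further and conclude that %MG and %MMS must be barred in lipodystrophy and replaced by MMSH. The protocol names MMSH but never defines it, so its independence from fat cannot be confirmed, and the group term or T2D-only analysis already removes the artefact.

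**What to change.** 1. Replace the statement that lipodystrophy patients are enrolled as sarcopenic and obese with one saying that sarcobesity status is set for every participant by the measurements in the section on sarcobesity indices, and never by diagnosis.
2. Make the obese T2D patients the main population for the binary Poisson analysis. This matches the specific part of the primary objective, which refers to patients with obesity and T2D. Alternatively, put a lipodystrophy group term in every pooled AGE model, Poisson and linear, outside the LASSO selection, and show the correlations by group.
3. Report the lipodystrophy group separately by component (grip strength, chair test, muscle mass in kg, %MG, %MMS), and note that %MG and %MMS depend on fat mass there.

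**Cost.** Protocol wording and analysis code, with no new measurement. The T2D-only binary analysis uses about 160 instead of 195 subjects; the alternative spends one degree of freedom. Correlations by group are less precise. For r = 0.2, power is 71.9% with 160 subjects (detectable r at 80% power 0.22) and 20.8% with 35 (0.46), so those in the 35 are descriptive. The pooled linear models with a group term keep all 195.

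### HbA1c, the only AGE measure labelled endogenous, is capped at entry in one group and not, as worded, in the other, so its pooled correlation with sarcobesity is hard to interpret

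*Combined protocol and SAP*

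**What the plan says.** Inclusion criterion 3 offers two routes into the study. The first is obesity with "type 2 diabetes in good metabolic control (HbA1c < 7.5" percent), diagnosed within 15 years. The second is a diagnosis of lipodystrophy recorded in the named registry. As the sentence is built, the HbA1c limit belongs to the first route only.

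The section on quantification of AGEs measures skin fluorescence and, in plasma, free AGEs and AGEs "bound to hemoglobin (HbA1c clinical practice test"). It describes the two plasma forms as "discriminating in exogenous (dAGEs) and endogenous AGEs, respectively". HbA1c is therefore the endogenous measure and free plasma AGE the dietary one; skin fluorescence is assigned to neither.

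The study design section says that lipodystrophy patients generally "have a more severe T2D phenotype, presumed to be sarcopenic, and have a high rate of endogenous AGE production".

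The sample size section takes 0.2 as the smallest correlation with the sarcobesity indices to be detected, and states that "195 subjects will be required to observe as significant the correlation between AGEs levels". It plans about 35 lipodystrophy patients and 160 with diabetes and obesity, and singles out no AGE measure.

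The statistical analysis section begins with Pearson or Spearman correlations for each AGE, then fits adjusted linear models and robust Poisson models. The named adjusters are age, sex and diabetes duration, with inflammation, Western diet adherence and physical activity as examples of further confounders. LASSO selects the variables. Lipodystrophy status is not named, and no analysis by group is specified.

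**The concern.** For 82% of the planned sample (160/195) the same variable is both entry filter and exposure. A correlation coefficient depends on the spread of the exposure, and here the upper part of that spread is removed by design. Free plasma AGE and skin fluorescence are not truncated directly, so correlations of different AGE measures are not on an equal footing within T2D-obesity.

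The remaining 18% enter, as worded, without the cap, and the protocol expects them to be high on endogenous AGE and poor on muscle. Pooling such a group with a capped group can create a correlation that reflects only which route the patient came in by.

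Two misreadings are at stake. A weak HbA1c correlation within T2D-obesity could be taken as evidence that endogenous AGEs matter little. A clear pooled correlation could be taken as a dose-response relation when it is a difference between groups. The plan says nothing that guards against either.

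**Working it through.** **1. The plan's own figure.** Inputs from the sample size section: α = 0.05 (two-sided assumed), power 80%, r = 0.2. By Fisher's z, n = [(1.960 + 0.842)/atanh(0.2)]² + 3 = (2.802/0.2027)² + 3 ≈ 194. The stated 195 is reproduced (power 80.2%). At n = 160 the power for r = 0.2 is 72%; at n = 35 it is 21%.

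**2. Effect of the cap within T2D-obesity.** Let u be the SD of HbA1c below 7.5% divided by the SD without a cap, for a normal distribution. If r is the correlation without the cap, the restricted value is r′ = r·u / √(1 − r² + r²u²).

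Example: with an uncapped mean of 7.5%, u = √(1 − 2/π) = 0.603 and r′ = 0.2 × 0.603 / √(0.96 + 0.04 × 0.364) = 0.122. Power at n = 160 is Φ(atanh(0.122) × √157 − 1.960) ≈ 34%.

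The mean and SD are assumptions, so a range is needed:

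| Assumed uncapped HbA1c | u | r′ (from 0.20) | Power, n = 160 |
|---|---|---|---|
| Mean 6.8–7.8%, SD 0.8–1.3 | 0.54–0.77 | 0.11–0.16 | 28–50% |
| Mean 6.3–6.5%, SD 0.6–0.8 | 0.84–0.94 | 0.17–0.19 | 57–67% |

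The second row matters because the plan takes half of the 160 with diabetes of less than one year's standing.

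**3. The slope.** With an assumed T2D mean of 7.3% and SD of 1.3, r = 0.20 corresponds to 0.2/1.3 = 0.154 outcome SD per 1% HbA1c. In simulation the slope in the capped T2D group was 0.15 to 0.16. The cap costs precision and does not bias a correctly specified linear slope.

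**4. Pooling with no association inside either group.** Score the outcome so that higher is worse. Let p = 35/195 = 0.179, so p(1 − p) = 0.147. Let Δx and Δy be the group differences in HbA1c and outcome. Then r = p(1 − p)·Δx·Δy / (SDx·SDy), with pooled SDs. Assume T2D HbA1c is normal with mean 7.3% and SD 1.3 before the cap (6.39% and 0.82 after), lipodystrophy SD is 1.3, and outcome SD within groups is 1.

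Example, lipodystrophy mean 8.0% and Δy = 1: Δx = 1.61, SDx = 1.113, SDy = √(1 + 0.147) = 1.071, so r = 0.147 × 1.61 / (1.113 × 1.071) = 0.20.

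| Lipodystrophy mean | Δy = 0.5 SD | Δy = 1 SD |
|---|---|---|
| 7.0% | 0.05 | 0.09 |
| 7.5% | 0.08 | 0.15 |
| 8.0% | 0.11 | 0.20 |
| 8.5% | 0.12 | 0.24 |

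At n = 195, r of 0.20 and 0.24 would be declared significant about 80% and 92% of the time.

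**5. Both effects together.** With an uncapped r of 0.20 in T2D (mean 7.3%, SD 1.3; about 0.13 after the cap), lipodystrophy means of 6.5–8.5% (SD 1.0–2.0) and outcome shifts from −0.5 to +1 SD, the simulated pooled r runs from 0.09 to 0.39. It is 0.24 to 0.39 when the lipodystrophy mean is 7.5% or more and the outcome is worse by 0.5 to 1 SD, the direction that the study design section presumes.

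**The case against.** The strongest reply is that this limits generalisation and is not an error. The T2D group is defined as well controlled, and its correlation is valid for that population. The r of 0.2 in the sample size section is not tied to an uncapped population. The adjusted regression slope survives the cap. Skin fluorescence and free plasma AGE are separate measures, and the expected result is a positive correlation in at least one compartment. All of this stands, and it keeps the point away from the primary aim.

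A reader might go further in three ways that the documents do not support.

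- *The planned HbA1c correlation is shrunk.* That holds within T2D-obesity relative to uncapped T2D. In the pooled 195 the direction is undetermined, as step 5 shows.
- *A dietary-versus-endogenous contrast is biased.* No such contrast is prespecified; each AGE is analysed separately. The risk lies in setting the separate coefficients side by side, which the labelling invites.
- *HbA1c should be dropped as an exposure.* That would remove the only measure labelled endogenous. Using it instead as a covariate in the other AGE models may over-adjust, because the plan treats it as part of the same glycation exposure.

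It is also fair to say that a group difference could affect pooled skin and plasma AGEs. What is particular to HbA1c is that the entry rule itself treats the two groups differently.

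**Conclusion.** The point holds as a matter of interpretation, and the plan should address it. The pooled HbA1c correlation combines a range-restricted within-group association with a between-group difference, and nothing in the analysis section separates them. An assumed r of 0.20 becomes about 0.11 to 0.19 within T2D-obesity. Group difference alone gives about 0.05 to 0.24 in the pooled sample, for lipodystrophy HbA1c means of 7.0 to 8.5% and outcome shifts of 0.5 to 1 SD.

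The structure comes from the text; the sizes do not. HbA1c means, SDs and shape in both groups, and the outcome shift, are assumptions. The pooled result also depends on reading criterion 3 as worded, with no HbA1c limit on the lipodystrophy route.

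**What to change.** Leave eligibility as it is and add a few sentences to the statistical analysis section:

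1. Keep HbA1c as an exposure. Report its correlations and adjusted slopes, with confidence intervals, separately for T2D-obesity and lipodystrophy.
2. In any pooled model containing HbA1c, include entry group as a forced covariate that LASSO cannot drop.
3. Label the T2D-obesity estimate as range-restricted by the entry criterion.
4. State that the size of the HbA1c correlation will not be compared with that of plasma or skin AGEs to judge endogenous against dietary origin.

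The cost is slightly more analysis, with no new patients or data. The lipodystrophy-only estimate will be imprecise: at n = 35 an observed r of 0.20 has a 95% interval of tanh(0.203 ± 1.960/√32), about −0.14 to 0.50, and power at r = 0.2 is about 21%. It should be presented as descriptive.
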